## 2.0 TRIAL DESIGN

### 2.1 Trial Design

Specific procedures to be performed during the trial, as well as their prescribed times and associated visit windows, are outlined in the Trial Flow Chart - Section 6.0. Details of each procedure are provided in Section 7.0 – Trial Procedures.

This is a single-site Phase II trial of intravenous (IV) pembrolizumab in subjects with non-small cell lung cancer (NSCLC) with PD-L1 positive ( $\geq 1\%$  by immunohistochemistry (IHC) 22C3 pharmDx test) and EGFR mutant tumors who have not been previously treated with a tyrosine kinase inhibitor (TKI). Approximately 25 subjects will be enrolled in this trial to examine the response to pembrolizumab in this TKI-naïve population. Subjects will all receive 200 mg every 3 weeks (Q3W). Assignment to pembrolizumab will be unblinded.

Subjects will be evaluated every 9 weeks (63 +/- 7 days) with radiographic imaging to assess response to treatment. All imaging obtained on study will be assessed using a modified Response Evaluation Criteria in Solid Tumors (RECIST) 1.1 for determination of objective response rate (ORR) and progression-free survival (PFS). Subjects will continue with the assigned study treatment until RECIST 1.1-defined progression of disease, unacceptable toxicity, intercurrent illness that prevents further administration of treatment, investigator's decision to withdraw the subject, subject withdraws consent, pregnancy of the subject, noncompliance with trial treatment or procedure requirements, administrative reasons, or the subject has received 35 trial treatments of pembrolizumab. Treatment may continue despite RECIST 1.1 defined progression if the subject is clinically stable and is considered to be deriving clinical benefit by the investigator. Adverse events will be monitored throughout the trial and graded in severity according to the guidelines outlined in the NCI Common Terminology Criteria for Adverse Events (CTCAE) version 4.0.

After the end of treatment, each subject will be followed for a minimum of 30 days for adverse event monitoring. After progression on pembrolizumab, patients will be asked to undergo an additional biopsy and blood draw and be followed through periodic follow-up visits and calls (every 60 days) for evaluation of duration of response with the EGFR TKI as well as survival follow up. Subjects will have post-treatment follow-up for disease status until death, withdrawing consent, or becoming lost to follow-up.

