In order to corroborate the results from the clinical trial, we conducted cell line experiments to evaluate potential immunomodulatory effects of EGFR TKIs, particularly with respect to the PD-1 pathway (Figure 1). Afatinib, an irreversible pan-HER inhibitor is associated with an  $IC_{50} < 1\mu M$  in H1975, HCC827 and Calu-3. Erlotinib, a reversible EGFR inhibitor, inhibits only HCC827 at this level. Neither TKI inhibits H460 at this level. The cell lines that were effectively inhibited by the EGFR TKI also saw a decrease in PD-L1 levels, confirming results from others (23). When studying TKI-resistant, non-small cell lung cancer cell lines, PD-L1 expression was not reduced by EGFR TKIs. The results mimic what we saw clinically, in which pembrolizumab was not an effective therapy in patients with EGFR sensitizing mutations after a prior EGFR TKI.

[figure not shown]

Figure 1: Western blot analysis of PD-L1 expression (PD-L1 mAb #13684, Cell Signaling Technology) in NSCLC cell lines in response to erlotinib and afatinib. NSCLC cell lines H1975 (EGFR L858R/T790M mutation), H460 (KRAS Q61H mutation), HCC827 (EGFR exon 19 deletion), and Calu-3 (*her2* amplification) were evaluated at

baseline and after 24 hours of exposure to 1  $\mu$ M erlotinib or afatinib. \* indicates an  $IC_{50} < 1 \mu$ M for the respective drug in that cell line.

Data from the KEYNOTE 024 trial showed that first-line treatment with pembrolizumab significantly improved progression-free and overall survival in patients with PD-L1 positive (>50%) non-small cell lung cancer. Pembrolizumab was also associated with a higher overall response rate and a longer duration of response than platinum-based chemotherapy. Patients with EGFR mutations were excluded from this study (37).

This study will be the first to our knowledge to evaluate the role of PD-1 inhibitors in EGFR mutant patients who have not yet received an EGFR TKI. After progression on pembrolizumab, patients will be asked to undergo an additional biopsy and blood draw and be followed through periodic follow-up visits and calls (~every 2 months) for evaluation of duration of response with the EGFR TKI as well as survival follow up. The goal of this clinical trial is to evaluate a treatment sequence in which EGFR mutant NSCLC patients receive pembrolizumab prior to an EGFR TKI.

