The End of Treatment and Follow-up visit procedures are listed in Section 6 (Protocol Flow Chart) and Section 7.1.5 (Visit Requirements). After the end of treatment, each subject will be followed for 30 days for adverse event monitoring (serious adverse events will be collected for 90 days after the end of treatment as described in Section 7.2.3.1). Subjects who discontinue for reasons other than progressive disease will have post-treatment follow-up for disease status until disease progression, initiating a non-study cancer treatment, withdrawing consent or becoming lost to follow-up. After documented disease progression each subject will be followed by telephone for overall survival until death, withdrawal of consent, or the end of the study, whichever occurs first.

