### **5.8 Clinical Criteria for Early Trial Termination**

Early trial termination will be the result of the criteria specified below:

1. Quality or quantity of data recording is inaccurate or incomplete
2. Poor adherence to protocol and regulatory requirements
3. Incidence or severity of adverse drug reaction in this or other studies indicates a potential health hazard to subjects
4. Plans to modify or discontinue the development of the study drug

In the event of Merck decision to no longer supply study drug, ample notification will be provided so that appropriate adjustments to subject treatment can be made.

Trial Period:	Screening Phase (Visit 1)	Treatment Cycles a								End of Treatment	Post-Treatment		
		1	2	3	4	To be repeated beyond 8 cycles					Discon	Safety Follow-up Visits b	
Treatment Cycle/Title:						5	6	7	8			3 months post tx	6 months post tx
Scheduling Window (Days):	-28 to -1		± 3	± 3	± 3	± 3	± 3	± 3	± 3	At time of Discon			
Full Physical Examination	X												
Directed Physical Examination		X	X	X	X	X	X	X	X	X	X	X	X
Vital Signs and Weight	X	X	X	X	X	X	X	X	X	X	X	X	X
ECOG Performance Status	X	X	X	X	X	X	X	X	X	X	X	X	X
12-Lead ECG	X												
Laboratory Procedures/Assessments: analysis performed by LOCAL laboratory													
Pregnancy Test – Urine or Serum □-HCG	X												
PT/INR and aPTT	X	X	X	X	X	X	X	X	X	X			
CBC with Differential	X	X	X	X	X	X	X	X	X	X			
Comprehensive Serum Chemistry Panel	X	X	X	X	X	X	X	X	X	X			
Urinalysis	X	X	X	X	X	X	X	X	X	X			
T3, FT4 and TSH	X	X	X	X	X	X	X	X	X	X			
Efficacy Measurements													

Trial Period:	Screening Phase (Visit 1)	Treatment Cycles a								End of Treatment	Post-Treatment		
		1	2	3	4	To be repeated beyond 8 cycles					Discon	Safety Follow-up Visits b	
Treatment Cycle/Title:						5	6	7	8			3 months post tx	6 months post tx
Scheduling Window (Days):	-28 to -1		± 3	± 3	± 3	± 3	± 3	± 3	± 3	At time of Discon			Approx.Q 2 months
Tumor Imaging	X				X			X		X	X	X	X
Brain Imaging	X 												
Tumor Biopsies/Archival Tissue Collection/Correlative Studies Blood													
Archival or Newly Obtained Tissue Collection 	X									X 			
Correlative Studies Blood Collection		X	X	X						X			

1. Brain imaging needed if clinically indicated
2. If patient has not had a biopsy or if tissue is exhausted, patient must undergo a new biopsy for the trial

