##### **7.1.1.5.3 Subsequent Anti-Cancer Therapy Status**

The investigator or qualified designee will review all new anti-neoplastic therapy initiated after the last dose of trial treatment. If a subject initiates a new anti-cancer therapy within 30 days after the last dose of trial treatment, the 30 day Safety Follow-up visit must occur before the first dose of the new therapy. Once new anti-cancer therapy has been initiated the subject will move into survival follow-up.

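### Section 5.6 follows patients by telephone for survival after progression, in conflict with Section 2.1, Section 7.1.5.4.1 and the flow chart, which provide the follow-up that TKI-phase ORR and PFS need

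*Combined protocol and SAP*

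**What the plan says.** Section 5.6 has two rules for the period after treatment. For patients who stop for reasons other than progression it provides "post-treatment follow-up for disease status until disease progression, initiating a non-study cancer treatment", among other end points. For everyone who progresses it says: "After documented disease progression each subject will be followed by telephone for overall survival". The same paragraph opens by referring the reader to the flow chart and Section 7.1.5 for follow-up procedures.

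Other sections differ:

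- Section 2.1: "Subjects will have post-treatment follow-up for disease status until death, withdrawing consent, or becoming lost to follow-up". After progression on pembrolizumab it provides "periodic follow-up visits and calls (every 60 days) for evaluation of duration of response with the EGFR TKI", as well as survival follow-up. Sections 1.0 and 4.2.1 say much the same.
- Section 7.1.5.4.1 (Survival Follow-up): clinic visits about every 2 months, with scans, until death, withdrawal or study end. Where follow-up is less frequent than every 3 months, a call covers vital status and current TKI use.
- Flow chart (Section 6.0): the tumor imaging row is marked at discontinuation, at 3 and 6 months after treatment, and in the later column headed "Approx.Q 2 months".
- Section 7.1.1.5.3: "Once new anti-cancer therapy has been initiated the subject will move into survival follow-up".

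Section 3.2 makes ORR, PFS and OS on the subsequent TKI the third secondary objective, in patients with a sensitizing mutation. Section 9.1 plans to compare these outcomes with data on treatment-naïve patients given a TKI. It states no time origin or baseline scan for the TKI phase. The only PFS and OS origin in 9.1 is randomization, and Section 7.1.1.7 says that the study is not randomized.

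**The concern.** A telephone call can establish that a patient is alive and taking a TKI. It cannot establish a RECIST response or a progression date. If a site works from 5.6, a patient who progresses on pembrolizumab and then starts a TKI contributes to OS but has no scheduled scan for TKI ORR or PFS. A patient who stops for toxicity and starts a TKI before progressing loses disease-status follow-up at that same moment. Scans not taken at the time cannot be supplied at the analysis.

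Section 4.2.1 describes evaluating the sequence of pembrolizumab followed by a TKI as the goal of the trial. The trial is small, at about 25 patients, so little information is available on the second half of that sequence to begin with.

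**Working it through.** The documents give no sample size, event count or power for the TKI phase, so there is no planned figure to reproduce for this point. The one powered endpoint is the primary ORR. With 25 patients the exact binomial rule of at least 5 responses gives P(X ≥ 5 | 0.10) = 0.0980 and P(X ≥ 5 | 0.26) = 0.8174, which agrees with the 81% in Section 9.6. That endpoint is measured on pembrolizumab and does not depend on follow-up after progression.

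The check itself is a comparison of the texts.

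| Place | Contact after progression | Scans after progression | Disease-status follow-up ends at |
|---|---|---|---|
| 5.6 | Telephone, for overall survival | None mentioned | Progression or non-study treatment, among others |
| 2.1 | Visits and calls every 60 days | Not named, but response on the TKI is to be evaluated | Death, withdrawal or loss to follow-up |
| 7.1.5.4.1 | Visits about every 2 months; call as fallback | Yes | Death, withdrawal or study end |
| Flow chart | Visits at 3 and 6 months, then about every 2 months | Marked in all 3 post-treatment columns, and at discontinuation | Not stated |

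1. *Mode of contact.* Telephone is the stated mode in 5.6. In 7.1.5.4.1 it is the fallback.
2. *Stopping point.* Section 5.6 stops disease-status follow-up at progression or at a new cancer treatment. Section 2.1 continues it to death. Both cannot be applied to a patient who starts a TKI.
3. *Consequence for objective 3.* Under the 5.6 sentence alone, the number of scheduled TKI-phase scans per patient is zero. Under 7.1.5.4.1 it is about one every 2 months.
4. *Routing.* Section 7.1.5.4 opens the imaging Follow-up Phase to patients who stopped for reasons other than progression, and 7.1.5.4.1 begins once those visits are complete. Section 7.1.1.5.3 separately sends anyone starting new therapy to survival follow-up. The destination for a TKI starter can therefore be found, but 7.1.5.4.1 does not itself say that such a patient, or one who has just progressed, enters directly.
5. *Fallback call.* Section 7.1.5.4 asks sites to make every effort to record TKI start, progression and death. The call in 7.1.5.4.1 lists only vital status and TKI use, so the progression date is missing from it.
6. *Baseline.* Section 7.1.5.3 places the discontinuation visit about 28 ± 7 days after the last dose, or before any new antineoplastic treatment if that is sooner. The flow chart marks imaging at discontinuation. A pre-TKI scan is thus normally scheduled, but no text names it as the baseline for TKI response.

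**The case against.** The best defence is that 5.6 describes how overall survival is ascertained, does not make the telephone the sole contact, and refers in the same paragraph to the sections that schedule the scans. Ending one phase of disease-status follow-up at new treatment also fits 7.1.1.5.3, which then moves the patient into survival follow-up, where scans continue. This defence shows that a careful reader can reach the scans. It does not remove the conflict: 5.6 gives its own rule for every patient who progresses, and that rule differs from the sections it refers to.

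Four stronger readings are tempting, and the documents do not support them.

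- *That progressors can reach scans only by starting new therapy.* The flow chart does not split its post-treatment columns by reason for stopping, and 2.1 follows disease status until death. The route through 7.1.1.5.3 also covers the very patients objective 3 concerns.
- *That there is no pre-TKI scan.* The discontinuation imaging normally supplies one.
- *That TKI-phase PFS could be overstated by half*, by adding the 6 months of average treatment in 1.0 to the roughly 12 months to TKI progression in 4.2.1 (6/12 = 50%). This joins a pembrolizumab-phase origin to a TKI-phase event. The PFS in 9.1 ends at the first documented progression, and its TKI sentence refers to outcomes after TKI therapy, so no section states that hybrid.
- *That the number of patients with sensitizing mutations measures the harm.* It shows at most who could contribute to objective 3, not who would be followed by telephone alone.

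**Conclusion.** The conflict is real and should be corrected. Read as written, 5.6 provides no scans for TKI ORR and PFS, while 7.1.5.4.1 and the flow chart schedule them and 2.1 expects response on the TKI to be evaluated. The damage depends on which text sites follow. The documents do not show this, so the number of patients affected cannot be given. The risk is confined to a secondary objective that has no power statement or decision rule; TKI-phase OS can still be obtained by telephone, and the primary endpoint is not affected.

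The gap in 9.1 is secondary. The TKI start date is already to be collected under 7.1.5.4, and the wording of 9.1 points towards counting from the TKI. What is missing is a written definition. Randomization as an origin is mainly a matter of terms, since 7.1.1.7 acknowledges that the label does not describe the design.

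**What to change.** 1. In 5.6, replace the telephone sentence and the stop at non-study treatment with the visit-and-scan follow-up already scheduled in 7.1.5.4.1 and the flow chart, consistent with 2.1.
2. In 7.1.5.4.1, state that patients who progress or start a TKI enter survival follow-up directly, in agreement with 7.1.1.5.3.
3. Add the progression date to the items collected at the fallback call, in line with 7.1.5.4.
4. As a supporting clarification in 9.1, start TKI-phase PFS and OS at the first TKI dose and name the last scan before that dose, normally the discontinuation scan, as the RECIST baseline. For the pembrolizumab phase, replace randomization with the date of first dose.

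The cost is wording in three sections and one data item on the fallback call, for about 25 patients. No scan is added beyond those that 7.1.5.4.1 and the flow chart already schedule.

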### **5.6.1 Discontinuation of Study Therapy after CR**

Discontinuation of treatment may be considered for subjects who have attained a confirmed CR that have been treated for at least 24 weeks with pembrolizumab and had at least two treatments with pembrolizumab beyond the date when the initial CR was declared. Subjects who then experience radiographic disease progression may be eligible for up to one year of additional treatment with pembrolizumab via the Second Course Phase at the discretion of the investigator if no cancer treatment was administered since the last dose of pembrolizumab, the subject meets the safety parameters listed in the Inclusion/Exclusion criteria, and the trial is open. Subjects will resume therapy at the same dose and schedule at the time of initial discontinuation. Additional details are provided in Section 7.1.5.5.

### **5.7 Subject Replacement Strategy**

A subject that discontinues from the trial will not be replaced.

### **5.8 Clinical Criteria for Early Trial Termination**

Early trial termination will be the result of the criteria specified below:

1. Quality or quantity of data recording is inaccurate or incomplete
2. Poor adherence to protocol and regulatory requirements
3. Incidence or severity of adverse drug reaction in this or other studies indicates a potential health hazard to subjects
4. Plans to modify or discontinue the development of the study drug

In the event of Merck decision to no longer supply study drug, ample notification will be provided so that appropriate adjustments to subject treatment can be made.

Trial Period:	Screening Phase (Visit 1)	Treatment Cycles a								End of Treatment	Post-Treatment		
		1	2	3	4	To be repeated beyond 8 cycles					Discon	Safety Follow-up Visits b	
Treatment Cycle/Title:						5	6	7	8			3 months post tx	6 months post tx
Scheduling Window (Days):	-28 to -1		± 3	± 3	± 3	± 3	± 3	± 3	± 3	At time of Discon			
Full Physical Examination	X												
Directed Physical Examination		X	X	X	X	X	X	X	X	X	X	X	X
Vital Signs and Weight	X	X	X	X	X	X	X	X	X	X	X	X	X
ECOG Performance Status	X	X	X	X	X	X	X	X	X	X	X	X	X
12-Lead ECG	X												
Laboratory Procedures/Assessments: analysis performed by LOCAL laboratory													
Pregnancy Test – Urine or Serum □-HCG	X												
PT/INR and aPTT	X	X	X	X	X	X	X	X	X	X			
CBC with Differential	X	X	X	X	X	X	X	X	X	X			
Comprehensive Serum Chemistry Panel	X	X	X	X	X	X	X	X	X	X			
Urinalysis	X	X	X	X	X	X	X	X	X	X			
T3, FT4 and TSH	X	X	X	X	X	X	X	X	X	X			
Efficacy Measurements													

Trial Period:	Screening Phase (Visit 1)	Treatment Cycles a								End of Treatment	Post-Treatment		
		1	2	3	4	To be repeated beyond 8 cycles					Discon	Safety Follow-up Visits b	
Treatment Cycle/Title:						5	6	7	8			3 months post tx	6 months post tx
Scheduling Window (Days):	-28 to -1		± 3	± 3	± 3	± 3	± 3	± 3	± 3	At time of Discon			Approx.Q 2 months
Tumor Imaging	X				X			X		X	X	X	X
Brain Imaging	X 												
Tumor Biopsies/Archival Tissue Collection/Correlative Studies Blood													
Archival or Newly Obtained Tissue Collection 	X									X 			
Correlative Studies Blood Collection		X	X	X						X			

1. Brain imaging needed if clinically indicated
2. If patient has not had a biopsy or if tissue is exhausted, patient must undergo a new biopsy for the trial
3. Patient has the option of undergoing an additional biopsy at end of treatment.

## **7.0 TRIAL PROCEDURES**

### **7.1 Trial Procedures**

The Trial Flow Chart - Section 6.0 summarizes the trial procedures to be performed at each visit. Individual trial procedures are described in detail below. It may be necessary to perform these procedures at unscheduled time points if deemed clinically necessary by the investigator.

Furthermore, additional evaluations/testing may be deemed necessary by the UCLA DSMB for reasons related to subject safety. In some cases, such evaluation/testing may be potentially sensitive in nature (e.g., HIV, Hepatitis C, etc.), and thus local regulations may require that additional informed consent be obtained from the subject. In these cases, such evaluations/testing will be performed in accordance with those regulations.

#### **7.1.1 Administrative Procedures**

##### **7.1.1.1 Informed Consent**

The Investigator must obtain documented consent from each potential subject prior to participating in a clinical trial.

###### **7.1.1.1.1 General Informed Consent**

Consent must be documented by the subject's dated signature or by the subject's legally acceptable representative's dated signature on a consent form along with the dated signature of the person conducting the consent discussion.

A copy of the signed and dated consent form should be given to the subject before participation in the trial.

The initial informed consent form, any subsequent revised written informed consent form and any written information provided to the subject must receive the IRB/ERC's approval/favorable opinion in advance of use. The subject or his/her legally acceptable representative should be informed in a timely manner if new information becomes available that may be relevant to the subject's willingness to continue participation in the trial. The communication of this information will be provided and documented via a revised consent form or addendum to the original consent form that captures the subject's dated signature or by the subject's legally acceptable representative's dated signature.

Specifics about a trial and the trial population will be added to the consent form template at the protocol level.

The informed consent will adhere to IRB/ERC requirements, applicable laws and regulations and UCLA DSMB requirements.

#### **7.1.1.2 Inclusion/Exclusion Criteria**

All inclusion and exclusion criteria will be reviewed by the investigator or qualified designee to ensure that the subject qualifies for the trial.

#### **7.1.1.3 Medical History**

A medical history will be obtained by the investigator or qualified designee. Medical history will include all active conditions, and any condition diagnosed within the prior 10 years that are considered to be clinically significant by the Investigator. Details regarding the disease for which the subject has enrolled in this study will be recorded separately and not listed as medical history.

#### **7.1.1.4 Prior and Concomitant Medications Review**

##### **7.1.1.4.1 Prior Medications**

The investigator or qualified designee will review prior medication use, including any protocol-specified washout requirement, and record prior medication taken by the subject within 28 days before starting the trial. Treatment for the disease for which the subject has enrolled in this study will be recorded separately and not listed as a prior medication.

